5.1.2. Randomization and Blinding

Not applicable.

5.2. Study Drugs

5.2.1. Epacadostat

5.2.1.1. Description and Administration

Epacadostat will be available as 25 or 100 mg tablets to be administered in a BID administration schedule. All BID doses of epacadostat will be taken PO in the morning and evening, approximately 12 hours apart without regard to food. If the morning or evening dose is missed by more than 4 hours, then that dose should be skipped, and the next scheduled dose should be taken at the usual time. Doses of epacadostat will be self-administered except on the days scheduled to be given at the study clinic (see Section 6).

Subjects should be counseled by the investigator to maintain strict adherence to the study regimen as prescribed and to keep a record of any missed doses. The subject will be instructed to bring all unopened, empty, and opened/partially used bottles of study drug at Day 1 study visits, at which time compliance will be assessed.

5.2.1.2. Supply, Packaging, and Labeling

Study drug tablets are packaged in high-density polyethylene bottles; no preparation is required. All Incyte study drugs will be color coded to avoid error.

All Incyte investigational product labels will be in the local language and will comply with the legal requirements of each country.

5.2.1.3. Storage

Bottles should be stored at room temperature, 15°C to 30°C (59°F to 86°F) and closed tightly to protect the tablets from humidity.

5.2.1.4. Instruction to Subjects for Handling Epacadostat

The subject must be instructed in the handling of study drug as follows:

- To store the study drug at room temperature.
- To only remove from the study drug bottle/kit the number of tablets needed at the time of administration.
- Not to remove doses in advance of the next scheduled administration.
- To make every effort to take doses on schedule.
- To report any missed doses.

- If the subject vomits after taking study drug, the subject should not take another dose.
- If the morning or evening dose of epacadostat is missed by more than 4 hours, then that dose should be skipped, and the next scheduled dose should be taken at the usual time.
- To keep study drug in a safe place and out of reach and sight of children.
- To bring all used and unused study drug kits to the site at each visit.

5.2.2. Pembrolizumab

5.2.2.1. Description and Administration

Pembrolizumab is available in single dose vials as a 100 mg/4 mL solution and 50 mg powder for injection. All subjects will receive pembrolizumab 200 mg via a 30-minute IV infusion Q3W on Day 1 of each 21-day cycle. Sites should make every effort to target infusion timing to be as close to 30 minutes as possible. At the end of the infusion, the line should be flushed with a sufficient quantity of normal saline. On days when epacadostat and azacitidine is administered in the clinic, epacadostat and azacitidine should be administered just before beginning the infusion of pembrolizumab.

Subjects may be administered pembrolizumab no less than 18 days between doses and no more than 3 days after the scheduled administration date. Doses given after the 3-day window are considered a dose delay. A maximum delay of 42 days between doses is allowed. If the delay is greater than 14 days, this must be discussed with medical monitor.

5.2.2.2. Supply, Packaging, and Labeling

Pembrolizumab vials will be affixed with a clinical label in accordance with regulatory requirements.

5.2.2.3. Storage

Pembrolizumab should be stored under refrigeration at 2°C to 8°C (36°F-46°F) and protected from light by storing it in the original package until time of use. Pembrolizumab should not be frozen or shaken.

5.2.3. Azacitidine

5.2.3.1. Description and Administration

Azacitidine is provided as a lyophilized powder in 100 mg single-use vials to be administered by SC injection or IV infusion. In the European Union, azacitidine will be administered SC only.

Five doses of azacitidine will be administered in the clinic during Cycles 1 through 3. Details for study drug administration in the treatment sequencing tumor biopsy cohorts (Cohorts A-3 through A-5) are presented in Table 5 and the study assessments tables (see Section 6). Subjects who remain on treatment beyond the Week 9 scan should continue to receive azacitidine until the second on-study scan (up to the Week 18 scan, for a maximum of 3 additional cycles) and then continue pembrolizumab and epacadostat as long as there is benefit. The 5 doses should be administered over the Day 1 to 7 period. Re-treatment with azacitidine (based on original

treatment assignment) along with pembrolizumab and epacadostat may be administered for subjects who had a CR, PR, or SD (for > 6 months) and later had evidence of PD while receiving pembrolizumab and epacadostat with medical monitor approval. Three additional cycles of azacitidine are pennitted.

5.2.3.2. Supply, Packaging, and Labeling

Azacitidine vials will be affixed with a clinical label in accordance with regulatmy requirements.

5.2.3.3. Storage

Umeconstituted vials of azacitidine should be stored at 25°C (77°F); excursions are pelmitted to 15°C to 30°C (59°F-86°F).

5.2.4. INCB057643

5.2.4.1. Description and Administration

Physical and chemical properties of iNCB057643 are summarized in the [INCB057643 IB](#). INCB057643 is fmmulated as 4 mg immediate-release tablets. The tablet is round and white to off-white and contains the active dmg substance along with compendialgrade excipients lactose monohydrate, sodium starch glycolate, and magnesium stearate.

Subjects will self-administer INCB057643 orally QD, as instmcted by the investigator. It will be administered in the clinic on the schedule outlined in Section 6. The starting dose in Part 1 is 4 mg. INCB057643 doses should be taken in the morning on an empty stomach when possible. Subjects should fast for approximately 2 hours before and 1 hour after INCB057643 administration, except on days when serial sampling is conducted, then subjects will fast at least 8 hours before or as indicated in Section 7.8. If a dose is missed by more than 8 hours, then the subject should skip that dose and take the next scheduled dose at the usual time. The sponsor may implement altemate administrat such as intelmediate doses, altemate dosing schedules, or altemate fmmulations, depending on [REDACTED] safety results.

5.2.4.2. Supply, Packaging, and Labeling

INCB057643 will be provided as 4 mg tablets packaged in high-density polyethylene bottles. No preparation is required. The investigational product labels will be in the local language and will comply with the legal requirements of each countyly.

5.2.4.3. Storage

INCB057643 dmg product should be stored at ambient conditions (15°C-30°C or 59°F-86°F).

5.2.4.4. Instruction to Subjects for Handling INCB057643

The subject must be instructed in the handling of INCB057643 as follows:

- To store INCB057643 at room temperature.
- To only remove from the study drug bottle the number of tablets needed at the time of administration.
- Not to remove doses in advance of the next scheduled administration.
- To make every effort to take doses on schedule.
- To fast for approximately 2 hours before and 1 hour after INCB057643 administration.
- If a dose is missed by more than 8 hours, then the subject should skip that dose and take next scheduled dose at the usual time.
- To report any missed doses.
- If the subject vomits after taking study drug, the subject should not take another dose; dosing should be resumed at the next scheduled dose.
- To keep study drug in a safe place and out of reach of children.
- To bring all used and unused study drug bottles to the site at each visit.

5.2.5. INCB059872

5.2.5.1. Description and Administration

Physical and chemical properties of INCB059872 are summarized in the [INCB059872 IB](#). INCB059872 is formulated as 1 mg tablets.

INCB059872 is only for use in the United States. Subjects will self-administer INCB059872 orally QD or QoD as instructed by the investigator. It will be administered in the clinic on the schedule outlined in Section 6. The starting dose in Part 1 is 1 mg QoD. INCB059872 doses should be taken in the morning on an empty stomach when possible. Subjects should fast for approximately 2 hours before and 1 hour after INCB059872 administration, except on days when serial [REDACTED] sampling is conducted, then subjects will fast at least 8 hours before [REDACTED] or as indicated in Section 7.8. If a dose is missed by more than 8 hours, then the subject should skip that dose and take next scheduled dose at the usual time. The sponsor may implement alternate [REDACTED] such as intermediate alternate dosing schedules, or alternate formulations, depending on [REDACTED] safety results.

5.2.5.2. Supply, Packaging, and Labeling

INCB059872 will be provided as 1 mg tablets packaged in high-density polyethylene bottles. No preparation is required. The investigational product labels will state "Caution: New Drug - Limited by Federal (or United States) law to investigational use."

5.2.5.3. Storage

Bottles of tablets should be stored in a refrigerator and maintained at a temperature between 2°C and 8°C (36°F-46°F).

5.2.5.4. Instruction to Subjects for Handling INCB059872

The subject must be instructed in the handling of INCB059872 as follows:

- To store INCB059872 in a refrigerator.
- To only remove from the study drug bottle the number of tablets needed at the time of administration.
- Not to remove doses in advance of the next scheduled administration.
- To make every effort to take doses on schedule.
- To fast for approximately 2 hours before and 1 hour after INCB059872 administration.
- If a dose is missed by more than 8 hours, then the subject should skip that dose and take next scheduled dose at the usual time.
- To report any missed doses.
- If the subject vomits after taking study drug, the subject should not take another dose; dosing should be resumed at the next scheduled dose.
- To keep study drug in a safe place and out of reach of children.
- To bring all used and unused study drug bottles to the site at each visit.

5.3. Treatment Compliance

Compliance with all study-related treatments should be emphasized to the subject by the site personnel, and appropriate steps should be taken to optimize compliance during the study. Compliance with epacadostat, INCB057643, and INCB059872 will be calculated by the sponsor based on the drug accountability documented by the site staff and monitored by the sponsor/designee (tablet counts). Subjects will be instructed to bring all study drugs with them to the study visits in order for site personnel to conduct tablet counts to assess study drug accountability. The drug accountability documentation will be used by the sponsor to calculate treatment compliance.

Pembrolizumab and azacitidine are administered as either IV or SC infusions by the site personnel. Receipt of infusions will be documented by the site staff and monitored by the sponsor or the sponsor's designee.

5-4_ Treatment Interruptions and Adjustments

5.4.1. Dose Modifications

Selections and modifications to the study drug regimen are planned for dose-escalation cohorts. Dose interruptions and modifications also may occur for individual study subjects. The identification of DLTs will define the doses used in Phase 2. Further, the occurrence of DLTs and other toxicities (related or unrelated to study drug) will guide decisions for treatment interruptions and discontinuation for individual subjects.

Intrasubject dose escalation will not be permitted.

5.4.1.1. Dose-Limiting Toxicity and Determination of Maximum Tolerated Dose

A DLT will be defined as the occurrence of any of the toxicities in Table 10 occurring up to and including Day 21 for Treatment Group A or Day 42 for Treatment Groups Band C. Only toxicities with a clear alternative explanation (eg, due to disease progression), transient (72 hours) abnormal laboratory values without associated clinically significant signs or symptoms based on investigator determination, irAEs of Grade 3 or higher that improve to Grade 1 or lower in < 5 days by appropriate care or with corticosteroid therapy can be deemed a non-DLT. All DLTs will be assessed by the investigator using the current CTCAE v4.03 criteria. Subjects who receive 2:75% doses of study drug (Treatment Group A: azacitidine [4 doses], epacadostat [32 doses], and pembrolizumab [1 dose]; Treatment Group B: INCB057643 [32 doses], epacadostat [32 doses], and pembrolizumab [1 dose]; Treatment Group C: INCB059872 [QD dosing, 32 doses; QoD dosing, 16 doses], epacadostat [32 doses], and pembrolizumab [1 dose]) at the level assigned or have a DLT will be considered evaluable for determining tolerability of the dose.

Individual subject dose reductions may be made based on events observed at any time during treatment with study drug; however, for the purposes of dose cohort escalation/de-escalation, expanding a dose cohort, and determining the MTD of the study drugs, decisions will be made based on events that are observed from the first day of study drug administration through and including the final day of Cycle 1 (Day 21) for Treatment Group A or Cycle 2 (Day 42) for Treatment Groups B and C. A lower MTD may subsequently be determined based on relevant toxicities that become evident after Day 21 (Treatment Group A) or Day 42 (Treatment Groups Band C).

Table 10: Definition of Dose-Limiting Toxicity

Toxicity

o!Unennatologic
 
 • Grade 4 (life-threatening) vomiting or diarrhea • Grade 4 electrolyte abnormality • Grade 4 systemic reaction • Any 2: Grade 3 no!Unematologic toxicity EXCEPT the following: 
 – Transient(72 hours) abno!mal laboratory values without associated clinically significant signs or symptoms. – ausea, vomiting, and diarrhea adequately controlled with medical therapy within 48 hours. – Grade 3 rash in the absence of desquamation, with no mucosal involvement, that does not require systemic steroids, and that resolves to Grade 1 within 14 days. – An event clearly associated with the underlying disease, disease progression, a concomitant medication, or comorbidity. – Asymptonnatic changes in lipid profiles. – Singular or nonfasting elevations in blood glucose (ie, blood glucose excursions will be considered toxicities if fasting blood glucose is elevated on 2 separate occasions). – Immtime-related adverse events of Grade 3 or higher that improve toGrade 1 in < 5 days by appropriate care or with corticosteroid therapy.

Hennatologic
 
 • 2: Grade 3 thrombocytopenia with clinically significant bleeding (requires hospitalization, transfusion of blood products, or other urgent medical intervention). • Grade 4 thrombocytopenia of any duration • Grade 4 neutropenia lasting > 3 days • 2: Grade 3 febrile neutropenia (absolute neutrophil cotmt < 1.0 x 10⁹/L and fever > 101°F/38.5°C). • Grade 4 neutropenia that does not recover toGrade 2 in3 days after interm!pting study dmg. • Grade 4 anemia not explained by underlying disease or some other concomitant disorder.

General
 
 • Subjects being unable to receive 2: 75% of study dmg doses during the DLT observation period because of toxicity, even if the toxicity does not meet DLT criteria defined above. 
ote:Exceptions include the DLT exclusions mentioned above.

MTD
 
 • 1 dose level below that at which 2: one-third of subjects in a palticular cohort has DLTs. Dose-limiting toxicity will be defined as the occull'ence of any of the toxicities in this table occUITing up to and including study Day 21.

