1.8.6. Risks From Combination Therapy

The combination of the immunotherapies epacadostat and pembrolizumab have the potential to precipitate more frequent, more severe, and/or new immune-related toxicities as compared with each individually. The addition of azacitidine, INCB057643, or INCB059872 to the epacadostat and pembrolizumab regimen may have the potential to increase irAEs due to their ability to re-express and up-regulate genes related to diverse immune pathways. The combination of azacitidine with pembrolizumab and epacadostat has been well-tolerated in Cohorts 1, 2A, 2B, and 3 with no DLTs observed to date in Part 1.

2- STUDY OBJECTIVES AND ENDPOINTS

2-L Study Objectives

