5.4.1.2. Criteria and Procedures for Dose Interruptions and Adjustments of Study Drug

Treatment with study drug may be delayed up to 2 weeks (14 days) to allow for resolution of toxicity. If only 1 of the 2 agents is suspected to be responsible for the toxicity, only the suspected agent should be held (while the other treatment continues). In some circumstances, it may be necessary to temporarily interrupt the combination as a result of AEs that may not have a cause attributable to a single drug or that may be the result of combined toxicity.

Subjects may resume treatment if no medical condition or other circumstance exists that, in the opinion of the investigator, would make further participation in the study unsuitable. The treating investigator should contact the sponsor to discuss the case of any subject whose treatment has been delayed for more than 14 days before restarting treatment with the study drugs.

Because subjects may enter the study with extensive pretreatment and/or severe bone marrow infiltration by the primary disease, these dose reduction rules are provided as guidelines (see [Table 15](#) through [Table 17](#)). Individual decisions regarding dose reduction should be made using clinical judgment and in consultation with the sponsor's medical monitor, taking into account relatedness of the AE to the study drug and the subject's underlying condition. Adverse events that have a clear alternative explanation or transient (≤ 72 hours) abnormal laboratory values without associated clinically significant signs or symptoms may be exempt from dose-reduction rules.

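### Protocol Section 5.4.1.1 lets a brief, symptom-free Grade 4 platelet count be classed as no DLT, Table 10 counts it as a DLT, and nothing says which prevails

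*Protocol*

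**What the plan says.** Protocol Section 5.4.1.1 starts from the table: "A DLT will be defined as the occurrence of any of the toxicities in Table 10". The next sentence gives a closed list of what may be classed as no DLT. One item is transient (72-hour) "abnormal laboratory values without associated clinically significant signs or symptoms based on investigator determination". It names no grade and no analyte. The grade wording in that sentence belongs to the immune-related item that follows it, which begins "irAEs of Grade 3 or higher that improve to Grade 1 or lower in < 5 days by appropriate care or with corticosteroid therapy can".

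Table 10, in its hematologic block, lists "Grade 4 thrombocytopenia of any duration". In its nonhematologic block, "Grade 4 electrolyte abnormality" is a bullet of its own. The table also has a 72-hour laboratory exception, but it is nested under the separate bullet for any other nonhematologic toxicity of Grade 3 or higher.

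Section 5.4.1.1.3 has the sponsor and investigators adjudicate high-grade events and agree escalation by telephone conference. Section 1.8.6 describes Group A Cohorts 1, 2A, 2B and 3 as well tolerated "with no DLTs observed to date in Part 1". SAP Section 8.2.2 lists DLTs by dose level and Section 8.2.5 counts subjects with any DLT. The SAP does not define a DLT.

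**The concern.** An exemption that turns on short duration cannot stand beside a criterion that applies whatever the duration. Suppose a subject has Grade 4 platelets without bleeding that recover in 48 hours. Table 10 makes this a DLT; the text allows it to be none.

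Determining the MTD, maximum tested dose or PAD is part of the Part 1 primary objective, and the 3 + 3 + 3 rule acts on counts of 0 to 3 events. One subject is enough to change the action. The DLT counts planned in the SAP inherit the same ambiguity, because a zero can mean that no qualifying event happened or that one was exempted.

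**Working it through.** **1. Length of the exemption.** The sign before 72 hours is not legible in the text of Section 5.4.1.1 available here. Section 5.4.1.2 uses parallel wording with the sign intact: "transient (≤ 72 hours) abnormal laboratory values without associated clinically significant signs or symptoms may be exempt from dose-reduction rules". I read the limit as 72 hours or less.

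**2. Where the passages collide.**
- Grade 4 platelets, no significant signs or symptoms, 72 hours or less: exemptible under the text, a DLT under Table 10. The conflict is explicit.
- Grade 4 electrolytes, same conditions: exemptible under the text, apparently a DLT under Table 10. This depends on the bullet standing outside the nested exceptions, as the table is laid out, and the bullet has no duration wording.
- Grade 4 neutropenia: no conflict, since Table 10 already requires more than 3 days.

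**3. Effect on the cohort decision** (rules from Protocol Section 4.1.1 and SAP Section 3.1.2; one disputed subject):

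| Exemption applied | Action | Table 10 applied | Action |
|---|---|---|---|
| 0/3 | escalate | 1/3 | expand to 6 |
| 1/3 | expand to 6 | 2/3 | de-escalate |
| 1/6 | escalate | 2/6 | expand to 9 |
| 2/9 | escalate | 3/9 | de-escalate |

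The last two rows also decide whether the dose meets the MTD definition (at most 1/6 or 2/9).

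**4. The plan's own figures.** With each group of three binomial at DLT rate p,

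P(de-escalate) = P(X≥2) + P(X=1) × [P(X≥2) + P(X=1) × P(X≥1)].

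At p = 0.20: 0.104 + 0.384 × (0.104 + 0.384 × 0.488) = 0.216. At 30%, 40%, 50% and 60% the formula gives 0.439, 0.650, 0.811 and 0.912. All five match Table 55 (21.6%, 43.9%, 65.0%, 81.1%, 91.2%), so the rule is being read as the sponsor reads it.

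**5. How often a cohort of three would contain a disputed event.** The documents give no rate, so r is assumed. P(at least one in three) = 1 − (1 − r)³:
- r = 5%: 1 − 0.95³ = 0.143
- r = 10%: 1 − 0.90³ = 0.271
- r = 20%: 1 − 0.80³ = 0.488

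This is an upper bound on the chance that the two readings part at the three-subject step. The exemption is discretionary, and a disputed event changes nothing if the subject already has another DLT or if the cohort already has two.

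**6. Outer limits for the whole rule.** Assume a 20% rate of other DLTs, and let q be the chance that a disputed event is a subject's only DLT-type event. If the exemption is always used, P(de-escalate) is 21.6%. If it is never used, the effective rate is 20% + q. For q = 5%, 10% or 20%, P(de-escalate) is then 32.5%, 43.9% or 65.0%. These contrast two extremes on assumed inputs and are not estimates for this trial.

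**The case against.** The strongest reply is that cohort decisions are not made site by site. The Section 5.4.1.1.3 conference looks at each high-grade event jointly, so in practice one reading would be applied to everyone. That stands as to process, but the section gives no rule for choosing between the passages. The note in Table 10 pointing back to the DLT exclusions sits in the row on receiving 75% of doses and settles nothing for platelets. Nor does the statement in Appendix E, under Amendment 1, that the thrombocytopenia and electrolyte criteria came from a regulator's request: it explains their origin and does not state precedence.

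The second reply is that little now depends on it. Enrollment has stopped, Groups B and C will not enroll, and no DLTs are reported in Part 1. This is largely right. Rewording the protocol will change no further escalation; what remains is how the DLT counts are reported and read.

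Four stronger readings are tempting, and the documents do not support them.
- A reader might infer that the conflict also runs the other way, because Table 10 exempts events such as "Grade 3 rash in the absence of desquamation, with no mucosal involvement, that does not require systemic steroids" that the closed list in the text omits. Those exceptions, with controlled nausea, vomiting and diarrhea, lipid changes and single glucose excursions, are inside Table 10's definition. Such events never become Table 10 toxicities, so they need no exemption.
- A reader might infer that brief Grade 4 thrombocytopenia is to be expected. Section 1.8.3 associates azacitidine with cytopenias but gives no grade, rate or duration, and Section 1.7.2 says the chosen dose should minimize hematologic toxicity. Scheduled Cycle 1 hematology in Table 30 falls on Day 1, Days 5-7 and Day 15, so showing recovery within 72 hours would usually need an unscheduled sample.
- A reader might infer that the statement of no DLTs is unreliable. Nothing shows that a disputed event occurred. A Grade 4 platelet value would appear in the planned hematology shift table (3.3.2) and Listings 2.8.1 and 2.8.7, although nothing there links it to a DLT decision.
- A reader might extend step 5 to six subjects. A six-subject cohort exists only after exactly 1/3, so an unconditional figure for six would not be the chance of a changed decision.

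**Conclusion.** The inconsistency is real and clear for platelets, and probable for electrolytes subject to table layout. It is an internal contradiction in the DLT definition, not a design choice. One disputed subject is enough to change the cohort action at 3, 6 or 9 subjects. How often that would happen cannot be derived from the documents: the 14%, 27% and 49% rest on assumed rates and bound the effect from above. With enrollment closed and no DLTs reported, the remaining consequence is that the reported DLT counts cannot be tied to a single definition. The conclusion rests on reading the limit as 72 hours or less and on the laboratory item having no grade or analyte limit.

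**What to change.** In the protocol, Section 5.4.1.1 and Table 10 must be reconciled so that there is one exclusion list, with each exclusion stating which Table 10 bullets it applies to. The text should refer to the table and not restate it. Which wording stands is for the sponsor.

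In SAP Section 8.2.2 and Listing 2.7.3, list by dose level any Day 1-21 event that meets a Table 10 bullet but was classed as no DLT under the laboratory exemption, and give the DLT count under each reading. If there were none, saying so closes the point.

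The cost is a few lines of wording and a few listing rows from data already collected, with no added subjects or procedures. The reported DLT count may become slightly less favourable.
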